2.13 Selection of the Study Eye

Only one eye will be designated as the study eye in each participant. For participants who meet eligibility criteria in both eyes during the screening phase, the eye with the higher reading center confirmed DRSS should be selected. If both eyes have the same score, the eye with the clearest lens and ocular media will be selected. If there is no objective basis for selecting the study eye, factors such as ocular dominance (better focus ability), other ocular pathology, and participant preference should be considered in making the selection. The final selection will be performed and documented by the investigator in discussion with the participant at BL and must not be changed during the study.

The non-study eye is eligible for treatment according to the standard of care treatments through the duration of the study.

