2.15.1 Schedule of Activities

Table 1 OTT166 201 Phase 2 DR Study: Schedule of Activities (Through Week 24 – Primary Endpoint)

Study Procedure	Screening Visit 1	Baseline (BL) Visit 2	Visit 3	Visit 4	Visit 5	Visit 6	Visit 7	Visit 8 ^a
Week	--	0	4	8	12	16	20	24
Day (visit window)	-21 to -1	1	29 ± 7 days	57 ± 7 days	85 ± 7 days	113 ± 7 days	141 ± 7 days	169 ± 7 days
Screening/Baseline (BL):								
Informed consent	X							
Inclusion/exclusion	X	X						
Medical and ophthalmic history	X							
Demographics	X							
Randomization		X						
Interval Medical Review:								
Review of concomitant medications	X	X	X	X	X	X	X	X
Continue study treatment ^b		X	X	X	X	X	X	
Ocular Assessmentsⁿ:								
Refraction and BCVA (ETDRS)	OU	OU	OU	OU	OU	OU	OU	OU
Slit lamp examination	OU	OU	OU	OU	OU	OU	OU	OU
Assessment of cornea ^c	OU	OU	OU	OU	OU	OU	OU	OU
Intraocular pressure ^d	OU	OU	OU	OU	OU	OU	OU	OU
Indirect ophthalmoscopy	OU	OU	OU	OU	OU	OU	OU	OU
4-wide or 7-field color fundus photography (mandatory) ^e	OU	OU	SE	SE	OU	SE	SE	OU
SD-OCT (widerfield if available)	OU	OU	SE	SE	OU	SE	SE	OU
OCTA (if available)	OU							OU
Wide field Fluorescein Angiography ^m	OU							OU
Gonioscopy	OU							OU

Study Procedure	Screening Visit 1	Baseline (BL) Visit 2	Visit 3	Visit 4	Visit 5	Visit 6	Visit 7	Visit 8 ^a
Week	--	0	4	8	12	16	20	24
Day (visit window)	-21 to -1	1	29 ± 7 days	57 ± 7 days	85 ± 7 days	113 ± 7 days	141 ± 7 days	169 ± 7 days
Non-Ocular Assessments:								
Physical examination ^f	X							
Vital signs ^g	X	X	X	X	X	X	X	X
Adverse events ^h	X	X	X	X	X	X	X	X
IP adherence review ^o			X	X	X	X	X	X
Laboratory Testing:ⁱ								
Hematology, blood chemistry, urinalysis, and HbA1c ^{j,l}	X							X
Pregnancy test, women of childbearing potential ^k	serum	urine	urine	urine	urine	urine	urine	urine

Abbreviations: BCVA: best corrected visual acuity; BL: baseline; ETDRS: Early Treatment Diabetic Retinopathy Study; HbA1c: glycosylated hemoglobin; OCTA: optical coherence tomography – angiography; OU: both eyes; SD-OCT: spectral-domain optical coherence tomography; SE: study eye.

- ^a Participants who are withdrawn from the study before Week 24/Visit 8 will be asked to return to the clinic to complete the end of study assessments.
- ^b Participants will continue to receive study treatment based on exam findings, AE review, and verification that rescue criteria are not met.

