- ^c Cornea health assessment following instillation of fluorescein stain, including epithelium and endothelium, for signs of toxicity.
- ^d Intraocular pressure should be measured at approximately the same time of day from visit to visit, if possible.
- ^e An FP and FA must be performed once a participant has been diagnosed with worse than mild PDR, ASNV, or new onset or worsening CI-DME in the study eye, and before rescue treatment is given.
- ^f May be performed at Visit 1 or Visit 2, including height, weight, and body temperature.
- ^g Vital signs (blood pressure and heart rate) will be measured after the participant has been sitting for 5 minutes at the screening visit. From baseline through end of study only blood pressure and heart rate will be measured.
- ^h AEs will be collected from the time the ICF is signed until early termination or the end of study visit. If a participant withdraws from the study, ongoing AEs will be followed to the end of study visit or until the participant withdraws consent.
- ⁱ All samples collected for laboratory assessments will be obtained prior to administration of study drug.
- ^j At visits at which FA is performed, urinalysis samples will be collected before FA in order to avoid false elevations in urine protein values.
- ^k For women of childbearing potential, a negative screening serum pregnancy test at Visit 1 is required before randomization. All women of childbearing potential will have a urine pregnancy test at each treatment visit starting at Visit 2 (Day 1); a negative urine pregnancy test is required before treatment is continued (randomized treatment, rescue treatment).
- ^l Refer to [Appendix 3](#) for clinical laboratory test details.
- ^m Screening Fluorescein angiography is valid for 3 months. Participants undergoing rescreen do not need IVFA repeated within 3 months of original angiogram.
- ⁿ Cornea should be assessed at the beginning before dilation.
- ^o Adherence to the dosing regimen should be monitored continuously and discussed with the participant at each visit. Sites are expected to intervene if there is suboptimal adherence or absence of data transfer and document the intervention in the patient dashboard.

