2.20 Statistical Considerations

2.20.1 *Statistical Hypotheses / Sample Size Determination*

This study is designed to evaluate the superiority of two doses of OTT166 (5 mg/day and 10 mg/day) compared to vehicle control for the treatment of DR. For each dose within each endpoint, the null hypothesis is that there is no difference between OTT166 and vehicle control or the difference is in the direction of inferiority of OTT166, and the alternative hypothesis is that there is a difference between OTT166 and vehicle control in the direction of superiority of OTT166. The vehicle control groups will be combined for all statistical analyses. No multiplicity adjustment is planned for this study.

The study will enroll approximately 210 participants randomized as described in [Section 2.14.3](#), 70 participants per group into each treatment arm and 35 participants per group into each matching vehicle control group and allowing for around 5% study attrition, aiming for at least 66 participants per treatment group and combined vehicle control group.

For the primary endpoint of improvement by at least 2 steps from BL on the DRSS at Week 24, completing 66 participants per group (active treatment BID, active treatment QID, combined vehicle control) through Week 24 will yield at least 90% power to demonstrate that the active treatment is superior to vehicle control using a 1-sided alpha of 0.05, provided that the true treatment effect (active treatment efficacy rate minus vehicle control efficacy rate) is at least 0.20 and the vehicle control efficacy rate is at most 0.06.

The sample size calculation was computed in nQuery 8.7 using a Chi square test for two proportions (continuity corrected).

2.20.2 *Outcome Measures*

The primary safety outcome measure of the study will be the proportion of participants who develop TEAEs through Week 24.

The primary efficacy outcome measure of the study will be the proportion of participants who have improved by ≥ 2 steps from baseline at Week 24 as determined by central reading center assessment using DRSS.

The secondary outcome measures are as follows:

- Proportion of participants developing worse than mild PDR (DRSS 65 and above) at Week 24
- Proportion of participants who develop ASNV at Week 24
- Time to development of PDR worse than mild (DRSS 65 and above)
- Proportion of participants who develop CI-DME at Week 24
- Time to development of CI-DME

- Proportion of participants developing VTC at Week 24

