Within participant treatment effects will also be assessed for the primary endpoint (DRSS step change of  $\geq 2$  steps) and key secondary endpoints (BCVA change, CST change, and development of CI-DME). Differences in outcomes from screening to Week 24 between eyes for participants in the two active treatment groups (OTT166 5 mg/day, OTT166 10 mg/day) will be compared using an appropriate paired data analysis: McNemar's test for dichotomous data and either a paired t-test or a Wilcoxon signed-rank test for continuous outcome data (changes from baseline). Data for eyes that were treated with anti-VEGF and/or laser will be imputed with LOCF from the time of starting treatment with anti-VEGF and/or laser. The earliest concomitant medication in the fellow eye with ATC4CD="SL01A" will be considered for anti-VEGF treatment in the fellow eye. Additionally, the first ocular concomitant procedure in the fellow eye will be considered for laser treatment. The ocular concomitant procedures will be reviewed and confirmed by the clinical team.

Associations between baseline covariates and compliance may be assessed graphically: monthly compliance may be presented as a series of boxplots for each baseline subgroup, by treatment group and overall, allowing for the observation of compliance trends within or between groups.

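### The exploratory study-eye versus fellow-eye comparison in SAP 4.10.4 can under-count CI-DME in the fellow eye, because that eye is scanned less often and LOCF carries a pre-event scan forward once it is treated

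*SAP*

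**What the plan says.** SAP 4.10.4 (Exploratory Analysis) plans a within-participant comparison of the eyes in the two active groups, from screening to Week 24. It covers the primary endpoint and the "key secondary endpoints (BCVA change, CST change, and development of CI-DME"). McNemar's test is used for dichotomous outcomes, and a paired t-test or signed-rank test for continuous ones. For treated eyes the rule is: "Data for eyes that were treated with anti-VEGF and/or laser will be imputed with LOCF from the time of starting treatment". It applies to either eye, is not limited to scheduled scans, and does not count treatment for edema as an event.

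The Schedule of Activities (Protocol 2.15.1, repeated in SAP 6.1) decides which eye is imaged. The row that begins "SD-OCT (widerfield if available" reads both eyes at Visits 1, 2, 5 and 8 and study eye only at Visits 3, 4, 6 and 7. Color fundus photography follows the same pattern. BCVA is measured in both eyes at every visit.

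Protocol 2.13 adds: "The non-study eye is eligible for treatment according to the standard of care treatments through the duration of the study". Footnote e of the schedule requires photography and angiography once a complication is diagnosed "in the study eye, and before rescue treatment is given". It sets no such requirement for the fellow eye and does not name OCT.

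Protocol 2.16.5 says OCT is done at every visit without naming an eye, but 2.16.1 refers the choice of eye to the schedule. It also says that all images obtained go to the central reading center.

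**The concern.** A paired test needs both members of the pair to have the same chance of showing the event. Here the study eye has six scheduled post-baseline OCTs and the fellow eye has two. The LOCF rule then turns unequal observation into unequal scoring. If a study eye is found to have CI-DME at Week 8 and is rescued, its Week 8 scan carries the event forward. If a fellow eye is found and treated at Week 8, its last scheduled scan is the baseline one, which shows no event. Being treated for the event removes it, mainly in the comparator eye, and that eye's CST is frozen before it worsened.

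The SAP presents this comparison as a treatment effect, and preventing CI-DME is a stated aim of the study (Protocol 2.1). Because only the active arms are included, no vehicle contrast would reveal the artefact.

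**Working it through.** **The plan's own figure.** None is given for the paired analysis. The only design calculation is for the primary endpoint: it "will yield at least 90% power" with 66 completers per group, "using a 1-sided alpha of 0.05", if the effect "is at least 0.20 and the vehicle control efficacy rate is at most 0.06". Rates of 0.26 and 0.06 give 56 per group uncorrected and 66 with the continuity correction, with power 90.3% at 66. The figure reproduces and does not bear on this point. It does fix the number of pairs: about 70 per active arm, 140 if the arms are pooled.

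**Step 1: scheduled OCTs after baseline.** Study eye: Weeks 4, 8, 12, 16, 20, 24, so a gap g = 4 weeks. Fellow eye: Weeks 12 and 24, so g = 12 weeks (visit windows ignored).

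**Step 2: share of onsets treated before the next scheduled OCT.** With onset uniform over 24 weeks and a delay of d weeks from onset to treatment, the share is max(0, 1 − d/g).

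| Delay d | Study eye | Fellow eye |
|---|---|---|
| 2 weeks | 1 − 2/4 = 50% | 1 − 2/12 = 83% |
| 4 weeks | 0% | 1 − 4/12 = 67% |
| 8 weeks | 0% | 1 − 8/12 = 33% |
| 12 weeks | 0% | 0% |

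**Step 3: observed fellow-eye rate.** Suppose detection and treatment fall on the 4-weekly visit grid. Four of the six visits (Weeks 4, 8, 16, 20) have no scheduled fellow-eye OCT, so 4/6 = 0.667 of events first appear there. Let t be the share of fellow-eye events treated at detection without a graded scan. Then observed rate = true rate × (1 − 0.667t).

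**Step 4: effect on a true benefit.** Assumptions: true risk 10% in the study eye and 20% in the fellow eye, independent eyes, exact McNemar test at one-sided 5% in the direction of benefit. With p_s the study-eye rate and p_f the observed fellow-eye rate, the discordant probabilities are p_s(1 − p_f) for study eye only and p_f(1 − p_s) for fellow eye only.

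| t | Observed fellow rate | Study only | Fellow only | Power, 70 pairs | Power, 140 pairs |
|---|---|---|---|---|---|
| 0 | 20.0% | 0.080 | 0.180 | 42% | 72% |
| 0.25 | 16.7% | 0.083 | 0.150 | 24% | 44% |
| 0.5 | 13.3% | 0.087 | 0.120 | 10% | 17% |

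**Step 5: effect with no true difference.** With 10% risk in both eyes, within-pair correlation 0.3 and 70 pairs, the fellow eye reads 8.3% / 6.7% / 3.3% at t = 0.25 / 0.5 / 1. The chance of declaring the study eye better falls from 2.1% to 0.75% / 0.21% / below 0.01%. Over true risks of 5% to 20%, the spurious difference runs from 0.8 to 13.3 percentage points.

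**Step 6: an opposing bias.** The CI-DME definition (Protocol 2.16.10; SAP 3.2.3) attaches no baseline condition to its CST > 325 µm limb, and the CST limit need be met in only one eye (Protocol 2.7). Let a share f of fellow eyes be above 325 µm at baseline and count as events. The net study-minus-fellow difference is r − [f + (1 − f) × r × (1 − 0.667t)]. At r = 10% and t = 0.5:
- f = 0: 10.0 − 6.7 = +3.3 points
- f = 5%: 10.0 − (5.0 + 6.3) = −1.3 points
- f = 10%: 10.0 − (10.0 + 6.0) = −6.0 points

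**The case against.** A reader might infer that harm is over-counted in the treated eye, or that the trial would produce a false harm finding. The documents do not support either reading. The study eye is scored by its own scans; it is the fellow eye that is under-counted. SAP 4.10.1 makes tests one-sided toward superiority of OTT166 unless otherwise stated, and SAP 4.11 allows no inferential statistics for safety. In the planned direction the artefact is conservative.

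Other points on that side stand in part:
- The loss is conditional. LOCF is not restricted to scheduled scans, and a fellow-eye OCT taken in routine care and graded would keep the event. None is required, though. Longer delays to treatment shrink the loss, to nothing at 12 weeks.
- The study eye can also lose events treated between visits: 50% at a 2-week delay, against 83% in the fellow eye. The gap narrows but remains.
- The endpoint is worded as at Week 24, when both eyes are imaged. On that reading untreated eyes are compared alike and only the LOCF path is left. If development means at any time, fellow-eye edema that comes and goes between scans is missed too. SAP 4.10.4 does not say which applies.
- The DRSS part is small. The paired outcome is improvement of at least two steps, so an eye frozen before worsening is usually a non-responder either way. Only an eye already improved at Week 12 would be misscored.
- The opposing bias in Step 6 is real. It is a second flaw in the same comparison, not a reason to leave the first.

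**Conclusion.** The point holds as an ascertainment flaw in an exploratory analysis. Followed as written, SAP 4.10.4 scores a fellow-eye CI-DME as no event when it arises and is treated between both-eye scans without a graded unscheduled OCT. The exposed gap is 12 weeks for the fellow eye against about 4 for the study eye. The likely consequence is a masked benefit or an unfavourable estimate for CI-DME and CST.

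The illustrated fall in power, 42% to 10% with 70 pairs and 72% to 17% with 140, rests on assumed risks, independence of the eyes, uniform onset, and half of fellow-eye events treated at detection without a graded scan. The documents supply none of these. The net direction cannot be stated: a few percent of fellow eyes thick at baseline would be enough to reverse the sign. The randomized between-arm analyses are untouched, and so is paired BCVA as far as its visit set goes. The change is worth making, but the trial's main conclusions do not depend on it.

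**What to change.** Amend SAP 4.10.4 before unmasking:

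1. For paired CI-DME and CST (and DRSS, where the effect is small), use in both eyes only the visits at which both are imaged: Visits 1/2, 5 and 8. BCVA needs no change to its visit set.
2. For paired CI-DME, restrict to pairs in which neither eye has CI-DME at baseline (no central fluid and CST ≤ 325 µm). This closes the opposing bias in Step 6.
3. For paired CI-DME, count an eye that starts anti-VEGF or laser for macular edema before Week 24 as an event, in either eye. This is in line with the composite handling of rescue in SAP 3.2.2, which SAP 4.10.1.2 extends to secondary proportions. Keep LOCF for treatment given for other reasons.
4. Extend the masked clinical review to the indication for fellow-eye anti-VEGF. The planned review covers ocular procedures only, and the ATC code that identifies anti-VEGF does not show why it was given.

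The cost is SAP wording, a small programming change and some record review, with no new assessments. The downsides are that interim study-eye scans go unused in this analysis (they stay in the between-arm ones) and some pairs are excluded. Treatment is also not a perfectly equal marker, because study-eye rescue follows listed criteria and medical-monitor consultation while fellow-eye treatment follows standard of care. The report should say so.

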#### 4.11 Safety Evaluation

All safety summaries and analyses will be based upon the Safety Analysis Set by treatment group (i.e., vehicle control doses (5% BID, 5% QID), vehicle control combined, active OTT166 doses (5% BID, 5% QID), and OTT166 combined). Safety summaries for age, gender, race and ethnicity subgroups will be provided. If any safety measurements are repeated at the same visit after dosing on Day 1, then the last (non-missing) value of any repeated measurements will be used in the descriptive statistics and in the calculation of changes from BL. No inferential statistics will be performed for safety variables.

##### 4.11.1 Adverse Events

Adverse events will be coded using the Medical Dictionary for Regulatory Activities (MedDRA) Version 24.1 or higher. Intensity and causality of AE will be evaluated by the investigator. The intensity of AE will be graded according to the criteria in Appendix 4 of the Protocol.

Incomplete start and end date of the AEs will be imputed as described in [Section 4.2.1](#).

Participants with multiple incidents of events for a given preferred term (PT) and system organ class (SOC) will be counted only once. Similarly, if participants experience multiple incidents of events for a given PT and SOC, the worst intensity will be used in the summaries presenting intensity, and the worst causality to study drug will be used in the summaries presenting causality, respectively.

Any missing intensity will be queried for completion and assessed by the Investigator based on AEs and serious AEs, as defined in Appendix 4 of the Protocol.

Any missing causality will also be queried for completion, and any events that still have missing causality in the final data will be deemed as 'Related'.

Adverse events of special interest (AESI) are defined as:

- Hypersensitivity reactions. Symptoms of hypersensitivity reactions (allergic reactions) include:
  - Rash
  - Wheezing and difficulty breathing

- Dizziness and fainting
- Swelling around the mouth, throat or eyes
- A fast pulse
- Sweating

Treatment-emergent adverse events (TEAEs) are defined as any adverse events occurring (onset date/time) at the time of or after dosing on Day 1. Where the AE start date is missing, AEs will be assumed to be treatment-emergent, unless there is clear evidence (through comparison of partial dates) to suggest that the adverse event started prior to the first dose of study treatment.

Adverse event summaries will be sorted in terms of decreasing frequency for SOC, and PT within SOC, in the overall group, and then alphabetically for SOC, and PT within SOC if there are any ties in frequency.

Analysis and reporting for adverse events will be based on TEAEs. An overall summary of TEAEs will include the number and percentage of participants in the following categories:

- Number and percentage of participants with TEAEs
- Number and percentage of participants with drug-related TEAEs
- Number and percentage of participants with TEAEs leading to discontinuation of study drug
- Number and percentage of participants with TEAEs leading to study discontinuation
- Number and percentage of participants with treatment-emergent serious adverse event (TESAEs)
- Number and percentage of participants with drug-related treatment-emergent serious adverse event (TESAEs)
- Number and percentage of participants with TESAEs leading to discontinuation of study drug
- Number and percentage of participants with TESAEs leading to study discontinuation
- Number and percentage of participants by intensity of TEAEs (mild, moderate, severe)
- Number and percentage of participants who experienced death from any cause
- Number and percentage of participants with AESIs

Summaries of TEAEs by treatment group, SOC, and PT will be presented for the following:

- All TEAEs
- Ocular TEAEs in the Study Eye
- Ocular TEAEs in the Fellow Eye
- Non-Ocular TEAEs
- Drug-related TEAEs
- TEAEs leading to discontinuation of study
- TEAEs leading to discontinuation of study drug

- All TESAEs
- Ocular TESAEs in the Study Eye
- Ocular TESAEs in the Fellow Eye
- Non-Ocular TESAEs
- Drug-related TESAEs
- TESAEs leading to discontinuation of study
- TESAEs leading to discontinuation of study drug
- TEAEs by intensity
- AESIs
- AESIs leading to discontinuation of study
- AESIs leading to discontinuation of study drug

By-participant listings of corresponding TEAE data will also be provided. Separate listings will be presented for TEAEs leading to discontinuation of study drug and treatment-emergent serious adverse events (TESAEs). Any AEs occurring between signing of ICF and dosing on Day 1 will be presented in a separate listing. All listings will be done by treatment group and participant, detailing verbatim, SOC, PT, start date, stop date (if resolved), intensity, seriousness, outcome, action taken with respect to study drug, and relationship to study drug. The AE onset will also be shown relative (in number of days) to the day of the first study drug administration.

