2.14.10.1 Permanent Discontinuation

In rare instances, it may be necessary for a participant to permanently discontinue (definitive discontinuation) study intervention. If study intervention is permanently discontinued, the participant may remain in the study for continued assessment of safety and efficacy outcomes.

Unscheduled visits may be performed as deemed appropriate by the investigator, in particular, in case of withdrawal due to an AE.

Participants *must* be withdrawn from the *study intervention* for any of the following reasons:

- If rescue therapy has been initiated
- Safety concerns for a participant by the investigator or the sponsor
- Vision threatening complication meeting rescue criteria and/or progression to worse than mild PDR with DRSS > 61
- Pregnancy (see [Section 2.17.4](#) for details)

Necessity to withdraw the participant from the study will be assessed case-by-case by the investigator in consultation with the medical monitor.

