2.15.2 Study Activities

After signing an informed consent, participants will be invited to a screening visit, Visit 1, to evaluate their eligibility for this study. Eligible participants with DR who meet all the inclusion criteria and none of the exclusion criteria will be randomized to treatment with one of two dosing frequencies (BID/QID) of 5% OTT166 or vehicle control. During the treatment period, participants will be monitored for AEs and concomitant medication, and undergo the assessments outlined in the SoA ([Section 2.15.1](#)).

The treatment period comprises Visits 2 to 8 (BL/Day 1 to End of Treatment/Study/Week 24), at which the primary endpoint will be assessed.

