2.18 *Adverse Events (AEs), Serious Adverse Events (SAEs), and Other Safety Reporting*

The definitions of AEs and SAEs can be found in [Appendix 3](#) and will conform to the current Medical Dictionary for Regulatory Activities (MedDRA) standard.

AEs will be reported by the participant (or, when appropriate, by a caregiver, surrogate, or the participant's legally authorized representative).

The Investigator and any qualified designees are responsible for detecting, documenting, and recording events that meet the definition of an AE or SAE and remain responsible for following up on all AEs reported during the study until resolution or until the end of the study.

2.18.1 *Time Period and Frequency for Collecting AE and SAE Information*

All AEs/SAEs will be collected from the signing of the ICF until end of study.

All SAEs will be recorded and reported to the sponsor or designee immediately and under no circumstance should this exceed 24 hours of learning of the event, as indicated in [Section 2.21.5](#). The investigator will submit any updated SAE data to the sponsor within 24 hours of it being available.

TEAEs will be defined as those AEs that occurred after first dosing and those existing pre-dose AEs that worsened in severity post-dose during the main treatment period until the end of study.

Investigators are not obligated to actively seek information on AEs or SAEs after conclusion of the study participation/the End-of-Study visit. However, if the investigator learns of any AE/SAE, including a death, at any time after a participant has been discharged from the study, and he/she considers the event to be reasonably related to the study intervention or study participation, the investigator must promptly notify the sponsor.

2.18.2 *Method of Detecting AEs and SAEs*

Care will be taken not to introduce bias when detecting AEs and/or SAEs. Open-ended and non-leading verbal questioning of the participant is the preferred method to inquire about AE occurrences.

2.18.3 *Follow-up of AEs and SAEs*

After the initial AE/SAE report, the investigator is required to proactively follow each participant at subsequent visits/contacts. All SAEs, and AEs of special interest (as defined in [Section 2.18.6](#)), will be followed until resolution, stabilization, the event is otherwise explained, or the participant is lost to follow-up (as defined in [Section 2.14.12](#)). Further information on follow-up procedures is provided in [Appendix 4](#).

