2.21.5 Adverse Events

AEs will be coded using MedDRA version 24.1 or higher and summarized by system organ class (SOC) and preferred term (PT). Analysis and reporting for AEs will be based on TEAEs. A TEAE is defined as an AE occurring (onset date/time) at the time of or after dosing on Day 1. AEs with missing start and/or end dates and/or times (if applicable) will be handled as described in the SAP.

All TEAEs will be listed for each participant. Separate listings will be presented for TEAEs leading to discontinuation of study drug and treatment-emergent serious adverse events (TESAEs). Any AEs occurring between signing of ICF and dosing on Day 1 will be presented in a separate listing. All listings will be done by treatment group and participant, detailing verbatim, SOC, PT, start date, stop date (if resolved), intensity, seriousness, outcome, action taken with respect to study drug, and relationship to study drug. The AE onset will also be shown relative (in number of days) to the day of the first study drug administration.

An overview of all TEAEs will be presented by treatment group. The overview will include the following:

- Number and percentage of participants with TEAEs
- Number and percentage of participants with drug-related TEAEs
- Number and percentage of participants with TEAEs leading to discontinuation of study drug
- Number and percentage of participants with TEAEs leading to study discontinuation
- Number and percentage of participants with TESAEs
- Number and percentage of participants with drug-related TESAEs

- Number and percentage of participants with TESAEs leading to discontinuation of study drug
- Number and percentage of participants with TESAEs leading to study discontinuation
- Number and percentage of participants by intensity of TEAEs (mild, moderate, severe)
- Number and percentage of participants who experienced death from any cause
- Number and percentage of participants with AESIs

Summaries of TEAEs by treatment group, SOC, and PT will be presented for the following:

- All TEAEs
- Ocular TEAEs in the Study Eye
- Ocular TEAEs in the Fellow Eye
- Non-Ocular TEAEs
- TEAEs leading to discontinuation of study
- TEAEs leading to discontinuation of study drug
- Drug-related TEAEs
- All TESAEs
- Ocular TESAEs in the Study Eye
- Ocular TESAEs in the Fellow Eye
- Non-Ocular TESAEs
- TESAEs leading to discontinuation of study
- TESAEs leading to discontinuation of study drug
- Drug-related TESAEs
- TEAEs by intensity
- AESIs

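### The safety tables do not separate adverse events before study-eye rescue from those after it, when study drug has stopped; a before/after flag would be a cheap improvement.

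*SAP*

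**What the plan says.** SAP 4.11.1 defines the event that drives the safety analysis: "Treatment-emergent adverse events (TEAEs) are defined as any adverse events occurring (onset date/time) at the time of or after dosing on Day 1". Protocol 2.21.5 agrees: "A TEAE is defined as an AE occurring (onset date/time) at the time of or after dosing on Day 1". Protocol 2.18.1 is the only place that names an end, and that end is the end of study. It also counts "those existing pre-dose AEs that worsened in severity post-dose during the main treatment period until the end of study", a clause that the other two definitions lack. Protocol 2.15.2 defines the treatment period by Visits 2 to 8, not by the participant's own last dose.

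Collection is equally wide. Protocol 2.18.1 says "All AEs/SAEs will be collected from the signing of the ICF until end of study", and the Schedule of Activities says "AEs will be collected from the time the ICF is signed until early termination or the end of study visit". The primary safety endpoint (SAP 3.2.1) is the proportion with a TEAE through Week 24.

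Rescue is anti-VEGF therapy and/or PRP laser (Protocol 2.14.9). In Protocol 2.14.10.1 the first reason for mandatory withdrawal of study drug is "If rescue therapy has been initiated". The same section says that after permanent discontinuation "the participant may remain in the study for continued assessment of safety and efficacy outcomes".

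Safety tables use the Safety Analysis Set, which groups participants by treatment actually received (SAP 4.4.1). None of the summaries listed in SAP 4.11.1 is restricted to time before rescue or time on drug.

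**The concern.** Read together, these rules mean that a study-eye event following an intravitreal injection or laser, with the drops already stopped, enters the TEAE count of the eye-drop group. Rescue is open to every arm, so the extra events fall on whichever arm is rescued more. If OTT166 works, that is likely to be vehicle. The vehicle TEAE proportion would then carry procedure events, and a local tolerability problem with the drops would look smaller against it. Safety is a primary objective, and study-eye tolerability of a drop given two or four times daily is a large part of it.

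The contrast with the rest of the SAP makes the gap visible. The primary estimand treats study-eye rescue as non-response (3.2.2). Time-to-event endpoints are censored at rescue (4.10.3). The observed-case analysis sets post-rescue data to missing, and the LOCF analysis uses the last pre-rescue value (4.10.2). Planned doses for compliance stop at end of treatment in rescued participants (4.9.2), and treatment duration stops at last dose (4.2). Exposure therefore ends while adverse-event counting continues.

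**Working it through.** **Plan's own figures.** The documents state no TEAE rate and no rescue rate for this trial, so there is nothing to reproduce. Group size is about 70 for each OTT166 arm and 35 + 35 = 70 for combined vehicle (SAP 4.13). What follows is illustration under stated assumptions.

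**Formula.** A participant adds to a TEAE proportion only once, so a post-rescue event matters only if it is that participant's first. For one group:

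rise = r × q × (1 − e)

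- r = proportion rescued in the study eye. Assumed 10% on vehicle and 4% on OTT166.
- q = proportion of rescued participants with a study-eye AE after rescue. Assumed 30% to 60%.
- e = proportion with an earlier study-eye TEAE. Taken as 18.2% and 14.3%, the study-eye rates at 2.5 mg/eye BID in the two Phase 1b studies (Protocol 2.5.1 and 2.5.2).

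**Study-eye TEAE proportion.**

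| | Low: q = 0.30, e = 0.182 | High: q = 0.60, e = 0.143 |
|---|---|---|
| Vehicle | 0.10 × 0.30 × 0.818 = 2.5 points | 0.10 × 0.60 × 0.857 = 5.1 points |
| OTT166 | 0.04 × 0.30 × 0.818 = 1.0 point | 0.04 × 0.60 × 0.857 = 2.1 points |
| Difference | 0.06 × 0.30 × 0.818 = 1.5 points | 0.06 × 0.60 × 0.857 = 3.1 points |

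The shift of 1.5-3.1 points, in favor of OTT166, is about 1.0 to 2.2 participants per 70.

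**Sensitivity to overlap.** The table assumes that rescued participants are no more likely than others to have an earlier study-eye TEAE. Protocol 2.16.9 describes the vision-threatening complications as AEs, and some of these are also objective rescue criteria. If half of rescued participants already had a study-eye TEAE, the shift would be 0.06 × (0.30 to 0.60) × 0.5 = 0.9 to 1.8 points. If all had one, it would be zero.

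**Any-cause TEAE proportion.** A second set of assumptions gives a range for the primary safety endpoint itself: rescue of 10/44 = 22.7% on vehicle and 4/44 = 9.1% on OTT166, a first TEAE after rescue in 10% to 50% of rescued participants without an earlier one, and an earlier TEAE in 30% to 50%. The difference in rescue is 6/44 = 13.6 points. The shift runs from 0.136 × 0.10 × 0.50 = 0.7 to 0.136 × 0.50 × 0.70 = 4.8 points, again in favor of OTT166. The two rescue rates are those of the DME and nAMD Phase 1b studies, used only to set a scale.

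**Equal rescue.** If r, q and e are the same in both groups, the difference does not move. Both proportions rise by the same amount, which dilutes the contrast but does not tilt it.

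**Scale of chance.** At 18.2% with 70 per group, the standard error of a difference is √(2 × 0.182 × 0.818 / 70) = 6.5 points. The study-eye shift is 1.5/6.5 = 0.23 to 3.1/6.5 = 0.48 of that.

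**The case against.** The strongest reply is that counting every event through Week 24 is the stated endpoint and a legitimate treatment-policy summary: it describes what happens to participants assigned to a regimen, rescue included. That stands, and it is why the all-TEAE tables should remain.

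Second, part of the information is already planned. Drug-related TEAE and TESAE tables are specified. The listings give onset day, action taken and relationship, and rescue is listed by participant (SAP 4.8). This is a real but partial mitigation. The primary safety endpoint is any-cause, the study-eye tables carry no causality restriction, and causality still missing at the end is deemed related. Onset is shown relative to first dose, so a reader would have to merge listings by hand to place events relative to rescue.

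Third, the size is modest and its inputs are assumed. The Phase 1b rescues are a weak guide. They were in CI-DME and nAMD, 12 of 14 came after the treatment phase, and none met the rescue criteria. This trial excludes CST above 325 µm and enrolls eyes in which PRP or anti-VEGF can be deferred for at least 6 months. No inferential safety comparison is planned. All of this stands and limits the weight of the point.

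Fourth, a reader might infer that crude pre-rescue counts should replace the all-TEAE counts as the basis of the tolerability conclusion. The documents do not support that. Stopping at rescue shortens follow-up more in the arm rescued more, which lowers that arm's crude rate for a reason unrelated to the drug. Pre-rescue results belong beside the full tables and need person-time.

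**Conclusion.** The point holds as a cheap improvement. The TEAE rule runs from Day 1 dosing to end of study without regard to rescue or last dose, study drug must have stopped once rescue starts, and no planned safety table separates the two periods. With rescue of 10% against 4% and a study-eye event in 30-60% after rescue, the study-eye comparison shifts by at most about 1.5-3.1 points, and by less where the triggering complication is already recorded as an AE.

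Two stronger readings go too far. One is that the rule is biased against OTT166, or certainly biased at all. Rescue applies to all arms, the direction depends on which arm is rescued more, and equal rescue produces no tilt. The other is that the shift is the plain product of rescue rate and event rate, 0.06 × (0.30 to 0.60) = 1.8-3.6 points. That counts participants who already had a study-eye TEAE. Attribution is also to the drop received, not the drop randomized.

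**What to change.** Keep the all-TEAE tables through Week 24 as the primary safety endpoint. In SAP 4.11.1:

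- Flag each TEAE by onset before, or on/after, the first study-eye rescue, using the start date already derived in SAP 4.8.
- Add a second flag relative to last dose, with a lag that the sponsor specifies, so that participants who stop for reasons other than rescue are covered.
- Show the TEAE proportion and the ocular study-eye TEAE and TESAE tables for pre-rescue (on-treatment) events beside the all-TEAE tables. Include exposure-adjusted rates, because follow-up before rescue may differ by arm.
- Tabulate post-rescue events separately.

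While editing, reconcile the worsening clause of Protocol 2.18.1 with the definitions in Protocol 2.21.5 and SAP 4.11.1.

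The cost is two derived flags from dates already collected and a few extra tables, with slightly lower pre-rescue counts. No new data are needed and participant management does not change. SAP 4.14 allows changes to be finalized before database lock.
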